2 SYNOPSIS

Name of Sponsor: Cumberland Pharmaceuticals Inc.	Finished Product: Atorvastatin injection	Active Ingredient: Atorvastatin Calcium		
Title of Study: Phase II, dose-ranging study to evaluate the efficacy dose response and pharmacokinetics of intravenous atorvastatin in hypercholesterolemic patients previously controlled with oral atorvastatin				
Study Center: Frontage Clinical Services, Inc.				
Expected Study Duration: 9 months	Phase of Development: II			
Objectives: 
• To propose intravenous doses of atorvastatin injection that adequately replace each dose level of oral atorvastatin• To describe the pharmacokinetic profile of atorvastatin injection administered by the intravenous route• To explore the pharmacokinetic profile of atorvastatin administered by the subcutaneous route• To assess the safety of the study drug administered by either the intravenous or subcutaneous route				
Methodology: Cohorts of thirteen subjects, composed from each of the commercially-prescribed levels of daily oral atorvastatin dosing (10, 20, and 40 mg), are treated for 15 days with open-label injectable atorvastatin. Dosing for each cohort is adjusted, if necessary as determined by the Sponsor based on either the Day 8 or Day 15 LDL-C values. Any cohort that does not remain below 125% of baseline LDL-C may be repeated at a dose level to be determined by the protocol. Pharmacokinetic profiles are summarized for multiple doses via the intravenous or subcutaneous routes and for a single dose via a subcutaneous route (sub-study). Safety is assessed by standard adverse event reporting and monitoring of serum levels of liver and muscle enzymes.				
Number of subjects (planned): Approximately 40 in the main study; estimated 26 in the sub-study				

Name of Sponsor: Cumberland Pharmaceuticals Inc.	Finished Product: Atorvastatin injection	Active Ingredient: Atorvastatin Calcium
Main criteria for inclusion:		
1. Adult between 18 and 65 years, inclusive. 2. On a stable dose of oral atorvastatin for at least 5 weeks prior to investigational treatment. 3. LDL-C value taken immediately at baseline is $\geq 75\%$ and $\leq 125\%$ of LDL-C taken one week prior.		
Main criteria for exclusion:		
1. A history of myopathy or rhabdomyolysis 2. Any hepatic impairment in the Investigator's judgement, including active gall bladder or biliary disorders 3. Screening aspartate aminotransferase (AST) or alanine aminotransferase (ALT) greater than two times the upper limit of normal 4. Uncontrolled hypothyroidism or diabetes mellitus 5. Alcohol consumption of more than two drinks per day, on average		
Investigational Medicinal Product (IMP), dose and mode of administration: Subjects taking 10 mg daily of oral atorvastatin at baseline start by receiving replacement treatment with 2 mg of intravenous atorvastatin daily. Based on monitoring of LDL-C levels, dosing in that group and subsequent groups may be adjusted in order to target an intravenous or subcutaneous dose for each baseline oral-dose level that controls LDL-C.		
A sub-study collects pharmacokinetic data following a single subcutaneous dose of atorvastatin injection.		
Duration of treatment: 15 days (+1 day for the sub-study)		
Criteria for evaluation:		
SAFETY EVALUATION 
• Adverse events• Changes in creatine phosphokinase, ALT and AST		
EFFICACY EVALUATION 
• Changes in LDL-C and high-density lipoprotein cholesterol (HDL-C)		

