5.4 Trial Rationale

This study is designed to propose non-inferior intravenous and subcutaneous doses of atorvastatin injection to temporarily replace stable, oral doses of 10, 20, and 40 mg. As expected and confirmed by the Phase I results, the systemic ratios of parent compound to active metabolites are altered with intravenous dosing as compared to oral. The pharmacokinetic profiles of each are further studied in this trial at the level of the individual patient to support both the dosing regimen and the safety profile of atorvastatin when administered parentally.

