8 STUDY DESCRIPTION

8.1 Study Design

- Phase II, open-label, single-center dose-ranging study.

- Three treatment cohorts of 13 subjects each are planned, potentially for each of the routes of administration (intravenously and subcutaneously). The different cohorts are composed of subjects taking three of the four commercially-prescribed levels of daily oral dosing: 10, 20, and 40 80 mg. Subjects are treated with daily doses of injectable atorvastatin intended to be non-inferior to the efficacy of their stable oral dose during the Lead-in Period.
- Enrollment of subjects into any one of the cohorts that does not prove to meet the primary endpoint, or otherwise shows a lack of efficacy, is terminated as soon as this determination is made, and a new cohort intended for 13 subjects is opened at an adjusted dose with intentions to meet the primary endpoint. See [Section 9.3.6.2.2](#).
- Subjects remain on the replacement treatment with atorvastatin for injection for 15 days, followed by a one-week follow-up period.
- Assessments include the following:
 - Pharmacokinetic (PK) profile evaluation of both the oral and IV dosing and, starting with Amendment 3, the SC dosing regimen.
 - Cholesterol (LDL-C) levels to assess efficacy
 - Safety assessment, including markers of rhabdomyolysis
- **Sub-study (Amendments 1 and 2 only):** If remaining on oral atorvastatin in the follow-up period, subjects that individually meet the study objective (Day 15 LDL-C \leq 125% of baseline level) may substitute a daily oral dose of atorvastatin for a subcutaneous dose of the same volume as the intravenous dose to which they were assigned. Plasma levels of atorvastatin and the two metabolites are measured for a 24-hour period to assess the pharmacokinetic parameters of the subcutaneous route.
- Schedules of assessments are summarized in [Table 9-1A](#) and [Table 9-1B](#) depending on the medication history of the subject when they entered the study.

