9.3.6.2.3 Subsequent Cohorts (20and 40 mg PO Atorvastatin)

Once two or more subjects from the 10 mg Lead-in group complete the study, the other cohorts can be opened to enrollment.

$LDL-C$ results from completed subjects in the 10 mg PO atorvastatin cohort provide information on the dose-response efficacy for the injectable route for atorvastatin that is helpful toward dosing the other Lead-in groups.

The targeted initial dose for each of the subsequent Lead-in cohorts is listed in [Table 9-4](#). However, any adjustments that were ultimately required for the dosing of the 10 mg PO cohort suggest that a similar adjustment is needed from the targeted doses for the other cohorts. Therefore, the starting dose for each subsequent cohort is adjusted accordingly by the sponsor prior to dosing the first enrolled subject of that treatment cohort.

With the activation of Protocol Amendment 3, dated 04Sep2019, one additional cohort is to be enrolled: Ten subjects that qualify for treatment following a lead-in period taking 20 mg oral atorvastatin are assigned to a daily dose of subcutaneous atorvastatin for the 15-day treatment phase.

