12.2 Subject Population(s) for Analysis

The safety population consists of all subjects who were enrolled and received at least a partial dose of IMP; no treated subjects will be excluded from the safety analysis population.

For the efficacy analyses, subjects will be stratified by their lead-in dose of oral atorvastatin. Defined by each of the three lead-in cohorts (10, 20, and 40 mg oral atorvastatin), the completed groups of thirteen subjects that 1) finish the two-week treatment period with intravenous atorvastatin, 2) provide a Day 15 LDL-C level, and 3) took the final targeted dose for that cohort comprise the three intravenous efficacy populations.

With the activation of Protocol Amendment 3, dated 04Sep2019, one additional efficacy population is defined. Ten subjects that qualify for treatment following a lead-in period taking 20 mg oral atorvastatin are assigned to a daily dose of subcutaneous atorvastatin for the 15-day treatment phase. Efficacy and pharmacokinetic outputs are calculated individually for this population.

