2	20 mg	4 mg IV	10 mg IV	13
3	40 mg	8 mg*IV	20 mg IV	13
4	20 mg	5 mg SC**		10

*Targeted starting doses for the cohort are shown; however actual starting doses may be adjusted pending findings from earlier cohorts **4th Cohort received 5 mg (0.5mL Atorvastatin) SC q 24 for 15 days.

Subjects remain on the replacement treatment with atorvastatin for injection for 15 days, followed by a one-week follow-up period.

Assessments include the following:

- Pharmacokinetic profile evaluation of both the oral and IV dosing
- Cholesterol levels to assess efficacy
- Safety assessment, including markers of rhabdomyolysis

Sub-study: For those subjects that are participating in the sub-study (only Cohorts 1, 2 and 3) will resume their Lead-in visit oral dose of atorvastatin on Day 16. On Day 22, subjects that individually meet the study objective (Day 15 LDL-C \leq 125% of baseline level) may replace a daily oral dose of atorvastatin by a SC dose of the same quantity as the IV dose to which they were assigned (see Table 2). Plasma levels of atorvastatin and the two metabolites are measured for a 24-hour period to assess the PK parameters of the SC route.

Table 2: Treatment Assignment – Sub-study

Cohort	Baseline Daily Dose of Oral Atorvastatin	Daily SC Atorvastatin Dose	Subjects*
1	10 mg	Same as daily final dose of IV Atorvastatin	≤ 13
2	20 mg	Same as daily final dose of IV Atorvastatin	≤ 13
3	40 mg	Same as daily final dose of IV Atorvastatin	≤ 13

* Subjects are from those meeting the study objective (Day 15 LDL-C $<$ 125% of baseline level) in the main study.

Per protocol amendment, version 02, subjects eligible for enrollment in the main study will include:

- Subjects taking oral atorvastatin prior to the study
- Subjects taking statins other than atorvastatin prior to the study
- Subjects not taking any statins prior to the study.

Based on the subject's prior use of atorvastatin, another statin, or no prior use of a statin, their progression through the screening and lead-in periods will follow the pathway as described in the following Study Procedures and description in the protocol (Section 9.1). For those subjects with prior oral atorvastatin use refer to Table 3A for the procedures. For subjects on a different statin or whom do not have prior use of a statin refer to Table 3B for the procedures.

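### The synopsis size of about 40 was not updated for the Amendment 3 subcutaneous cohort (the current design has 49 evaluable subjects), and the subcutaneous scope in Protocol 5.4, 7 and 8.1 is wider than the one cohort enrolled

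*Protocol*

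**What the plan says.** **Size.** The Protocol synopsis gives the planned number as "Approximately 40 in the main study; estimated 26 in the sub-study". Its methodology paragraph describes "Cohorts of thirteen subjects, composed from each of the commercially-prescribed levels of daily oral atorvastatin dosing (10, 20, and 40 mg").

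**The added cohort.** Under Amendment 3, Protocol 9.3.6.2.3 states that "one additional cohort is to be enrolled: Ten subjects that qualify for treatment following a lead-in period taking 20 mg oral atorvastatin" are assigned to 15 days of SC dosing. Protocol 12.2 adds that "one additional efficacy population is defined" for them. SAP section 4, Table 1 (the main-study assignment table) lists four cohorts of 13, 13, 13 and 10, and its footnote records that "4th Cohort received 5 mg (0.5mL Atorvastatin) SC q 24 for 15 days".

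**SC scope elsewhere.** Protocol 8.1 says "Three treatment cohorts of 13 subjects each are planned, potentially for each of the routes of administration (intravenously and subcutaneously"). Protocol section 7 lists SC pharmacokinetic parameters for three final treatment cohorts. Protocol 5.4 describes the study as "designed to propose non-inferior intravenous and subcutaneous doses of atorvastatin injection" to replace oral 10, 20 and 40 mg. Protocol section 6 and SAP section 2 are narrower: replacement doses are to be proposed for the IV route only, and SC is confined to exploring pharmacokinetics and assessing safety.

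**Success and power.** Protocol 12.3.2 and SAP 5.6 call a cohort successful when eleven or more subjects meet the LDL-C criterion (the Protocol adds the HDL-C criterion). Protocol 12.1 and SAP 4.4 claim 80% power with 13 subjects. Protocol 12.1 applies this to IV or SC dosing, SAP 4.4 to injectable dosing generally.

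**The concern.** The synopsis was extended to cover repeated SC dosing, since its methodology and product paragraphs both mention that route, but its subject count was not. Protocol 15.2 lists the number of subjects treated among the substantive matters that need an amendment and ethics approval, so the headline figure should match the cohorts described in the body.

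The scope mismatch affects what may be concluded. A reader of 5.4 would expect the study to support non-inferior SC replacement doses at three oral levels, whereas the sections that define the cohorts give repeated SC dosing at one level only. A success rule and power statement written for 13 subjects also sit beside a cohort of 10 with no word on whether they apply to it.

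**Working it through.** **1. Reproduce the stated size.** Inputs: three lead-in levels and 13 per cohort (synopsis, 8.1, SAP Table 1).

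- 3 × 13 = 39, which agrees with a stated figure of about 40.
- The sub-study subjects come from these same IV cohorts (8.1, 8.4.4; SAP Table 2), so the 26 is a subset and is not added.

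**2. Add the Amendment 3 cohort.** Input: 10 SC subjects (9.3.6.2.3, 12.2, SAP Table 1).

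- 39 + 10 = 49 evaluable subjects at final doses.
- 49 − 40 = 9, and 9/40 = 22.5%.

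**3. What 49 leaves out.** Under 9.3.6.2.2 a cohort whose dose is adjusted restarts with 13 new subjects intended, and 10.2 allows discontinued subjects to be replaced. The efficacy populations in 12.2 admit only subjects who took the final dose. Subjects at superseded doses and replacements therefore come on top of 49, and no allowance is stated.

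**4. SC evidence by oral level.**

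| Oral lead-in | Repeated SC dosing with Day 15 LDL-C | Single SC dose (sub-study) |
|---|---|---|
| 10 mg | none | pharmacokinetics only |
| 20 mg | 10 subjects | pharmacokinetics only |
| 40 mg | none | pharmacokinetics only |

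The sub-study schedule has no LDL-C measurement after the SC dose, and the sub-study is closed under Amendment 3 (8.4.4).

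**5. Section 7 against the SAP.** SAP section 3 separates two lists: repeated injectable dosing in four final cohorts, and a single SC dose in three. Protocol section 7 does not say single dose for its three SC cohorts and gives the repeated-dose SC cohort no place of its own.

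**6. The success rule at n = 10.** P(X ≥ 11) = 0 for any response rate, because X cannot exceed 10. SAP 5.6 also names only IV doses in its responder summary.

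**7. The power statement at n = 10.** Inputs from 12.1: SD 0.15, margin 0.10, true change 0. Alpha and sidedness are not stated; one-sided 0.05 is assumed here. Normal approximation: power = Φ(0.10√n / 0.15 − 1.645).

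- n = 13: Φ(2.404 − 1.645) = Φ(0.759) = 77.6%, near the stated 80%.
- n = 10: Φ(2.108 − 1.645) = Φ(0.463) = 67.8%.

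| Basis | n = 13 | n = 10 |
|---|---|---|
| Normal, one-sided 0.05 | 77.6% | 67.8% |
| t test, one-sided 0.05 | 73.2% | 61.8% |
| t test, one-sided 0.10 | 85.0% | 76.6% |
| Two one-sided t tests, 0.05 each | 47.0% | 28.2% |

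On all four bases, power at n = 10 is below 80%.

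**The case against.** The strongest reply is that this is a single un-updated line. The figure is marked approximate and fits the IV part, the sections that govern enrolment and analysis (9.3.6.2.3, 12.2, SAP Table 1) agree on four cohorts, and the synopsis itself discloses that cohorts may be repeated. An analyst would not mistake which cohorts exist. That stands, and it is why the point is an inconsistency and not a miscalculation.

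It does not dispose of the point. The synopsis count cannot be read as deliberately IV-only when the same synopsis describes repeated SC dosing, and neither 5.4 nor 8.1 is a count that can be excused as approximate.

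Section 7 has a partial defence: its SC list can be read as the single-dose sub-study, which is how SAP section 3 words it. The Protocol should then say so.

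Four stronger readings are tempting and are not supported:

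- **That 78 subjects are planned** (2 routes × 3 cohorts × 13). No total of 78 is stated, and 8.1 makes the second route only a possibility. The defect in 8.1 is that it leaves open an option the later sections have narrowed.
- **That the synopsis promises SC doses at every level.** It speaks of adjusting dosing to "target an intravenous or subcutaneous dose for each baseline oral-dose level that controls LDL-C". The word *or* is satisfied by IV doses at all three levels.
- **That the SC objectives cannot be met.** The formal SC objectives are exploratory pharmacokinetics and safety, which the single-dose data and the 20 mg cohort can serve. Only the wider claim in 5.4 lacks data.
- **That the number of subjects at superseded doses can be forecast.** This needs an IV dose-response relation, which the documents do not give.

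**Conclusion.** The concern holds as an inconsistency left by Amendment 3. The synopsis size covers 39 IV subjects and omits the 10 in the SC cohort. The current design has 49 evaluable subjects, 22.5% above the stated 40, with superseded-dose and replaced subjects additional and unquantified. The total of 49 is a sum of stated cohort sizes; the documents do not print it.

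Protocol 8.1 and section 7 need reconciling with the single SC cohort of 10. The claim in 5.4 of non-inferior SC doses has no repeated-dose LDL-C data behind it at 10 or 40 mg and goes beyond the stated objectives. At 20 mg, ten subjects cannot meet a rule requiring eleven, and power is about 62 to 68% at an assumed one-sided 0.05 with the Protocol's SD and margin.

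The analysis of the three IV cohorts is not affected.

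**What to change.** 1. **Synopsis:** state 49 evaluable subjects at final doses in the main study (39 IV, 13 at each of three lead-in levels, plus 10 SC after 20 mg lead-in). Add that subjects at superseded doses and replacements are additional, and that sub-study subjects are drawn from the IV cohorts.
2. **Protocol 8.1:** assign the three cohorts of 13 to the IV route, as SAP section 4 does, and name the single SC cohort of 10.
3. **Protocol section 7:** separate single-dose SC pharmacokinetics in the three IV cohorts from repeated-dose SC pharmacokinetics in the 20 mg cohort, in line with SAP section 3.
4. **Protocol 5.4:** limit the SC statement to one exploratory cohort at the 20 mg lead-in level, with no non-inferior SC dose claim for 10 or 40 mg.
5. **Protocol 12.1 and 12.3.2, SAP 4.4 and 5.6:** state that the 11-of-13 rule and the n = 13, 80% power statement do not apply to the SC cohort. Report its responders out of 10 and its mean LDL-C change descriptively.

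The cost is wording. The stated size becomes larger and the SC claim narrower, with no subjects beyond those already in the design. The SAP footnote describes SC dosing in the past tense; if the Protocol can no longer be amended, record the same clarifications in the SAP and the final report under the route in SAP 5.12.

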4 LIST OF ABBREVIATIONS AND DEFINITION OF TERMS

Abbreviation	Definition or Term
AE	Adverse Event
AUC _{inf}	area under the curve to infinity
ALT	alanine aminotransferase
AST	aspartate aminotransferase
BUN	Blood urea nitrogen
°C	Celsius, degrees
CBC	Complete Blood Count
CFR	Code of Federal Regulations
CK	Creatine Kinase
Cl	Clearance
C _{max}	maximum serum concentration
CMP	Comprehensive metabolic profile (serum biochemistry profile)
CPI	Cumberland Pharmaceuticals Inc.
CRF	Case Report Form
dL	deciliter
eCRF	Electronic Case Report Form
EU	European Union
FDA	Food and Drug Administration
GCP	Good Clinical Practice
HBV	Hepatitis Virus B
HCV	Hepatitis Virus C
HDL-C	high density lipoprotein cholesterol
HIV	Human Immunodeficiency Virus
HMG-CoA	3-hydroxy-3-methylglutaryl-coenzyme A
ICH	International Conference on Harmonization
IMP	Investigational Medicinal Product
IRB	Institutional Review Board
IV	intravenous
K _{el}	elimination rate constant
kg	kilogram
LDH	Lactate dehydrogenase
LDL-C	low density lipoprotein cholesterol
Mg	milligram

Abbreviation Definition or Term

MI	myocardial infarction
mL	milliliter
mmHg	millimeters of mercury
N	Number
NPO	Nil per os (nothing by mouth)
NOAEL	no observed adverse effect level
PK	pharmacokinetics
PO	Per os (by mouth)
q.d.	Once daily
SAE	Serious Adverse Event/Experience
SC	Subcutaneous
SCr	Serum creatinine
T _{1/2}	elimination half-life
TEAE	Treatment-emergent adverse event
ULN	upper limit of normal
VDss	Volume of distribution at steady state
WD	withdrawn

5 INTRODUCTION

This study is to be performed in accordance with Good Clinical Practice (GCP), the ethical principles that have their origin in the Declaration of Helsinki, Title 21 of the Code of Federal Regulations Parts 50, 56 and 312, and the International Conference on Harmonization E6.

5.1 Background Information

Cumberland Pharmaceuticals Inc. is developing atorvastatin injection for use in patients where an injectable route of atorvastatin administration is preferred.

Oral atorvastatin is currently approved for a number of indications, including the treatment of hyperlipidemia and the reduction of risk of myocardial infarction, stroke, revascularization procedures and angina ([Lipitor Package Insert 2018](#)). Atorvastatin injection is initially under study for treatment of hypercholesterolemia in patients where the intravenous (IV) or subcutaneous (SC) route is preferable to the oral route.

Statins, i.e., 3-hydroxy-3-methylglutaryl-coenzyme A (HMG-CoA) reductase inhibitors, are a class of drugs to treat patients with hypercholesterolemia and for secondary prevention of coronary artery disease and stroke. Statins are among the most potent cholesterol lowering drugs available, yet only commercially available in oral formulations.

An injectable formulation of atorvastatin would allow for continuation of atorvastatin therapy in patients whenever enteral administration is not possible. There is evidence that abrupt discontinuation of statin therapy in patients with acute vascular disease results in adverse outcomes like cardiac events and higher mortality ([Endres 2008](#), [Daskalopoulou 2008](#), [Schouten 2007](#)). Patients that may potentially benefit from injectable statin administration include: (1) individuals on an established statin regimen who are hospitalized and listed as *nil per os* (NPO) such as those who are intubated, sedated, unconscious, or perioperative; (2) classes of acutely vulnerable patients such as those experiencing stroke, acute coronary syndrome, and certain types of myocardial infarction (MI) who may obtain protective effects from immediate statin administration; and (3) patients at high-risk of vascular events prior to and immediately following surgery.

Atorvastatin injection is being developed by Cumberland Pharmaceuticals Inc. (CPI). The current formulation of atorvastatin injection is a 10 mg/mL (40 mg/4mL) liquid for injection, available in a glass vial.

Several Cumberland-sponsored nonclinical studies of atorvastatin injection have been conducted. No adverse trends were seen in a repeat-dose canine toxicity study, a rabbit-ear venous irritation study, or hemolysis and flocculation studies with human plasma/serum. The highest doses of

atorvastatin injection caused elevated liver enzymes, a result consistent with high dose oral atorvastatin. The dog toxicity study determined a no observed adverse effect level (NOAEL) of 20 mg/kg/day atorvastatin injection.

In a Phase 1 clinical trial in healthy volunteers, a preliminary pharmacokinetic profile for the parent compound and the two active metabolites was established for the intravenous delivery route. No major safety concerns were identified.

The current study is intended to further define the pharmacodynamic properties of atorvastatin and metabolites when delivered intravenously or subcutaneously, and to propose a dosing regimen to meet efficacy and safety objectives in changing from an oral to an injectable route. A single dose of atorvastatin will also be given by the subcutaneous route in a sub-study and initial pharmacokinetic data will be collected for subjects enrolling under Amendments 1 or 2 of the study protocol. In Protocol Amendment 3, dated 04Sep2019, subjects taking oral atorvastatin change to a subcutaneous route for the treatment phase rather than an intravenous route.

